Document: Protocol and SAP

Study title: Neuronal and Behavioral Effects of Implicit Priming in Obese Individuals

NCT: NCT02347527

Document date: 7/02/2015

COMIRB Protocol

COLORADO MULTIPLE INSTITUTIONAL REVIEW BOARD
[name] [contact] [contact]

Project Title (COMIRB): Effects of implicit priming on food cue responses

Principal Investigator: [name]

Co-Investigator: [name].

Version date: 7/02/15

I. Hypotheses and Specific Aims:

The development of novel strategies to promote weight loss and maintenance is critical, given the increasing prevalence of obesity in the United States. Greater responsiveness to high-calorie foods may lead to greater intake of these foods, contributing to obesity. The main aim of the current pilot project is to inform the development of a potential weight loss tool by assessing how priming pictures of food affects ratings. To achieve this goal, participants will be assigned to either the (a) active group or (b) control group. In the active group, images of high- and low-calorie foods will be paired with implicitly presented (below perceptual threshold) images of either negative or positive valence (high-calorie paired with negative; low-calorie with positive). For example, an ice cream image primed with an image of a pizza with cockroaches on it, or a piece of fruit primed with an image of a smiling child. During this task, participants will not perceive these primed pictures (although they will be told that they are there), and will rate each food picture on whether the food is "healthy" or "not healthy". Those in the control group will be primed with neutral images. Brain responses to food pictures will be recorded before and after the priming task. Participants will rate pictures of foods before and after the priming task on how much they "desire to eat" each food. In addition, participants will eat a buffet-style breakfast and lunch after the priming task, to see how the task affects food intake.

II. Background and Significance:

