Exclusion criteria include: history of major medical condition affecting weight/metabolism; medications affecting weight; pregnancy; bariatric surgery; history of psychiatric/eating disorder; current dieting; those following a vegan or vegetarian diet; and fMRI exclusions (claustrophobia, metal in body, weight>300 lbs). Those at risk for eating disorders (score >20 on the Eating Attitudes Test [EAT-26]) will also be excluded.

C. Study Design and Research Methods

Initially, subjects will be pre-screened over the phone to assess eligibility. Eligible and interested subjects will be asked to arrive to the screening visit in a fasted. Following informed consent and demographics, participants will undergo a screening day including baseline measures and a 1-day, run-in eucaloric diet, prior to the fMRI study day. The run-in diet's caloric value will be

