determined through body composition measurements taken at baseline, using BodPod. Also during the initial baseline visit, participants will be asked to complete several food/eating-related questionnaires: Eating Attitudes Test (EAT-26), Disgust Scale -R, Three Factor Eating Questionnaire (TFEQ), Power of Food Scale (PFS), and Food Craving Inventory (FCQ). In addition, participants will complete two brief surveys, one in which they will rate food pictures on “desire to eat” and another in which they will categorize foods as “healthy” or “unhealthy.” After baseline measurements, participants will be randomly assigned to either the (a) active group or (b) control group in a 1:1 ratio. In the active group, images of high- and low-calorie foods will be paired with implicitly presented (below perceptual threshold; presented for 20 ms) images of either negative or positive valence (high-calorie paired with negative; low-calorie with positive). During this task, participants will not perceive these primed pictures (although they will be told that they are there), and will rate each food picture on whether the food is “healthy” or “not healthy.” Those in the control group will be primed with neutral images. The priming task will be completed during functional magnetic resonance imaging (fMRI), to assess brain responses during the task. Additionally, participants will view a series of food pictures during fMRI recording immediately before and after the priming task. Following the priming/categorization task, participants will again complete the food picture ratings outside the MRI. Following this, participants may stay for an additional 4 hours, across which they will consume a buffet-style lunch to measure food intake. Subjects will also complete visual analog scale (VAS) ratings on their subjective hunger, fullness, and prospective food consumption at baseline, prior to, and 30/60 minutes after each ad libitum meal. The entire session will take approximately 2-6 hours. Participants may also be asked to return 3-5 days later to complete the food picture ratings again, which will take approximately 10 minutes.

D. Description, Risks and Justification of Procedures and Data Collection Tools:

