Response and reaction time data for the response to each picture during the priming task will be collected via the presentation software (Eprime 2.0). These data will be imported into SPSS version 21 (IBM Corp., Armonk, NY). Responses will be split into high- and low-calorie foods, which will be compared using paired-samples t-tests. The food ratings are performed using the ImageRate program ²⁸, which saves results in a spreadsheet. These ratings (for pre- and post-priming) will be imported into SPSS and split into high- and low-calorie foods. The change between session 1 and session 2 will be assessed for both high- and low-calorie foods using paired-samples t-tests. Group comparisons (control vs. active) will use independent-samples t-tests and the interaction between high- and low-calorie foods (difference in the change between each category) will also be tested.

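### Desire-to-eat ratings: the between-arm t-test is valid but does not use the pre-priming rating as a covariate, and the paired pre-post tests beside it are not marked as descriptive

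*Combined protocol and SAP*

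**What the plan says.** Section I states the main aim as informing a possible weight-loss tool "by assessing how priming pictures of food affects ratings". Section IV.A lists the desire-to-eat ratings first among three primary outcomes.

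Section IV.F sets out the analysis of these ratings in three sentences:
- Data preparation: "These ratings (for pre- and post-priming) will be imported into SPSS and split into high- and low-calorie foods".
- Comparison over time, without reference to arm: "The change between session 1 and session 2 will be assessed for both high- and low-calorie foods using paired-samples t-tests".
- Comparison of the arms, together with the calorie contrast as a further test: "Group comparisons (control vs. active) will use independent-samples t-tests and the interaction between high- and low-calorie foods (difference in the change between each category".

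No covariate is named. The response variable of the between-arm t-test is not named either, although the reference to a difference in change points to change scores. Nothing says which test answers the main question, or whether the paired tests are run by arm or with the arms pooled. The repeated-measures ANOVA later in IV.F is for the fMRI maps, and the t-tests at its end are for eating-behaviour measures, so neither covers the ratings.

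On timing, Section IV.C places a first set of desire-to-eat ratings at the initial baseline visit: "participants will complete two brief surveys, one in which they will rate food pictures on". Allocation comes later: "After baseline measurements, participants will be randomly assigned to either the (a) active group or (b) control group in a 1:1 ratio". The same section says that "participants will undergo a screening day including baseline measures and a 1-day, run-in eucaloric diet, prior to the fMRI study day", and that on the scan day "participants will view a series of food pictures during fMRI recording immediately before and after the priming task". The ratings are then repeated outside the scanner. Section IV.D (Food rating task) gives the scale as 0-100.

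**The concern.** There are two issues, and the first carries more weight.

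**Precision.** A rating on the same scale as the outcome is available from before randomisation. A change score fixes the coefficient of that rating at 1. A linear model estimates the coefficient and usually gives a smaller variance for the arm difference. In a pilot meant to inform a larger study, precision on the main aim is worth having.

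**Role of the paired tests.** A pre-post change mixes any effect of priming with whatever else moves ratings in both arms. Candidates are rating the same pictures a second time and seeing food pictures in the scanner. The run-in diet is another, if the pre-rating analysed is the one from the screening visit. The neutral-prime control arm is there to remove such drift. Because the plan gives the tests no order, a significant paired change could be reported as a finding about priming.

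**Working it through.** The plan states no sample size, SD, pre-post correlation, effect size or significance level for the ratings, so there is no figure of its own to reproduce. Every input below is assumed and is shown over a range.

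**1. Change score against ANCOVA, one food category**

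Inputs: equal pre and post variance σ², pre-post correlation r, total sample size N split 1:1 (the ratio is in IV.C). The variance per participant that enters the arm difference is:
- change score: 2σ²(1 − r)
- ANCOVA: σ²(1 − r²), times 1 + 1/(N − 4) for estimating the slope with a normal covariate

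Ratio, ANCOVA to change = [(1 + r)/2] × [1 + 1/(N − 4)].

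The last factor is 1 + 1/36 = 1.028 at N = 40 and 1 + 1/16 = 1.0625 at N = 20.

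| r | (1 + r)/2 | 20 per arm | 10 per arm |
|---|---|---|---|
| 0.3 | 0.65 | 0.67 | 0.69 |
| 0.5 | 0.75 | 0.77 | 0.80 |
| 0.7 | 0.85 | 0.87 | 0.90 |
| 0.9 | 0.95 | 0.98 | 1.01 |

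Simulation (40,000 runs) agreed to within about 0.01. Dividing 20 by the ratio gives the number per arm at which a change-score test would match ANCOVA with 20 per arm: 29.9, 25.9, 22.9 and 20.5.

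The gain ends where the ratio is 1, that is at r = 2(N − 4)/(N − 3) − 1. This is 72/37 − 1 = 0.95 at N = 40 and 32/17 − 1 = 0.88 at N = 20.

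**2. The high-minus-low contrast**

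Let c_w be the correlation between high- and low-calorie ratings on the same occasion, and c_x the same correlation across occasions. The pre-post correlation of the difference is r_D = (r − c_x)/(1 − c_w). With r = 0.7 and c_w = 0.5, at 20 per arm:
- c_x = 0.50: r_D = 0.20/0.50 = 0.40, ratio 0.72
- c_x = 0.35: r_D = 0.35/0.50 = 0.70, ratio 0.87
- c_x = 0.30: r_D = 0.40/0.50 = 0.80, ratio 0.925

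The gain for the interaction can thus be larger or smaller than for one category (0.87).

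**3. Paired test under drift alone**

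Assume no priming effect and a shift common to both arms of d SDs of the change. The rejection rate of a two-sided 5% paired t-test comes from the noncentral t distribution with n − 1 degrees of freedom and noncentrality d√n.

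| Participants in the paired test | d = 0.1 | d = 0.2 | d = 0.3 |
|---|---|---|---|
| 10 (one arm of 10) | 5.9% | 8.8% | 13.6% |
| 20 (one arm of 20, or two of 10 pooled) | 7.1% | 13.6% | 24.7% |
| 40 (two arms of 20 pooled) | 9.5% | 23.5% | 45.7% |

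If the tests are run by arm with 20 per arm and d = 0.3, the pattern of a significant active arm and a non-significant control arm occurs in 0.247 × (1 − 0.247) = 19% of trials.

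In the between-arm comparison the common shift subtracts out. In simulation with a 0.3 SD shift, the change-score t-test and ANCOVA both rejected in about 5% of trials.

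**The case against.** The strongest reply is that nothing here is an error. The randomised comparison is planned, it is valid, and on the natural reading it already uses baseline by subtraction. That stands. A reader might infer from the missing covariate that baseline is ignored, or that the arm comparison is biased or has the wrong error rate. The documents support neither inference, and the cost is precision only.

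The gain may also be slight. Each score summarises many of the 90 pictures described in IV.D, so a high r is plausible, although no value is given. At r of 0.7 to 0.9 with 20 per arm the variance saving is 2% to 13%, and at r = 0.9 with 10 per arm ANCOVA is marginally worse. This stands too: adjustment is cheap, not free.

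On the paired tests, a reader might infer that the plan means to treat a pre-post change as evidence of priming. Section IV.F does not say so. It says only that the change will be assessed, and it moves straight to the arm comparison. Nor is 46% this trial's error rate: it needs pooled arms, 40 participants and a drift of 0.3 SD, none of which the documents state. What remains is that no sentence gives the arm comparison precedence.

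Finally, the run-in diet is a source of drift only if the analysed pre-rating is from the screening visit. The food rating task in IV.D can be read as placing the ratings and the priming task in one sitting. A scan-day rating before priming would still be usable as a covariate, but the argument from the diet would fall.

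**Conclusion.** The point holds as an improvement that should be made, not as a fault in validity. Under equal pre and post variances, adjusting for the pre-priming rating cuts the variance of the arm difference by about a third at r = 0.3 and by about an eighth at r = 0.7 with 20 per arm. It cuts almost nothing at r = 0.9, where with 10 per arm there is a loss of about 1%. For the high-minus-low contrast the gain can go either way relative to a single category. Sample size and correlation are not in the documents, so the actual gain cannot be stated. If the between-arm test were on the post-priming rating alone, which the text does not exclude, the comparison would be with 1 − r² before the slope factor, and the gain would grow with r.

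The secondary point is that a paired change is not an estimate of the priming effect, whether tested by arm or pooled. How often it would mislead depends on a drift that the documents do not quantify. Confidence is medium, because the text is clear on what is omitted but every size rests on assumption.

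**What to change.** (a) State in IV.F that the between-arm contrast is the inferential analysis of the ratings. For each food category, fit a linear model of post-priming rating on arm and pre-priming rating. For the interaction, model the post-priming high-minus-low difference on arm and the pre-priming high-minus-low difference. State which of these three contrasts leads. Say that sessions 1 and 2 are the pre- and post-priming ratings, and on which day the pre-rating is taken.

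(b) Report paired changes by arm as descriptive, as mean change with a 95% CI, and not as evidence of a priming effect.

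The cost is wording only, since the covariate is already collected. The statistical price is one degree of freedom and a variance cost of about 1/(N − 4), so a very small sample with a very high correlation may gain nothing.

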The proposed study is the first step in a larger goal to identify a technique to promote healthier eating that would neuronal responses to food cues and food intake behaviors. This pilot study will investigate an implicit priming task, in which positive or negative images are presented immediately prior to food images, but are not consciously perceived. This pilot study will identify whether implicit priming can alter ratings of food pictures on “desire to eat.” In addition, we will assess how priming alters brain responses to food and food intake. The results of this study will inform the development of a larger study to implement this approach as an intervention to promote healthier eating habits.

Previous studies have found implicitly pairing target pictures with pictures or words of positive/negative valence (e.g., pairing a flower picture with the word “stench”) lead to increased liking/disliking of the target picture²³. These effects may be quite durable, as one study found alterations in ratings of target pictures to remain 2 months later²⁴. As such, this approach has the potential to reduce the appeal of hedonic foods and increase the appeal of healthier foods, which could encourage reduced intake of high-calorie foods in favor of low-calorie foods, promoting weight loss and weight loss maintenance.

III. Preliminary Studies/Progress Report:

As this is a pilot study, there are no preliminary data to report. If the aims of the project are achieved, the next step would be to use the results to inform development of an intervention to promote healthy eating. The subsequent study will also investigate the effects of this intervention on neuronal responses and subsequent food intake.

IV. Research Methods

A. Outcome Measure(s):

Primary outcomes in this study will be:

- 1) Ratings of food pictures on “desire to eat”
- 2) Brain responses to food pictures
- 3) Food intake

B. Description of Population to be Enrolled:

The study will include adult participants between ages 21-65. Participants older than 65 years of age will not be included to avoid potential effects of aging on food perceptions.

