Ad-Libitum Food Intake: Ad-libitum intake will be measured during a lunch meal served after the fMRI priming task. The purpose of this method will be to use weigh and measure methods to quantify food intake and macronutrient content of the diet directly. Specifically, a research dietitian will work with the subject to provide meals that replicate, to the extent practical/possible, usual meals consumed by the subject. Subjects will be asked to not consume any other food or beverages and to maintain usual activities. All meals will be prepared by the metabolic kitchen of the Anschutz Health and Wellness Center (AHWC) and will be offered with 30% more food than predicted requirements. Subjects will be instructed to eat what they want and that they can request more of any food. This design should neither restrict intake, nor encourage over consumption. Food intake and macronutrient composition will be determined by ‘weigh and measure’ methods by the dietary staff of the AHWC.

Body composition: Fat mass and fat-free body mass will be measured at baseline, prior to the fMRI study day, using BodPod at the AHWC. The BodPod system employs air displacement plethysmography to determine body composition, through calculating body volume and measuring body mass³³.

Demographic measures: Participants will be asked to report their age, ethnicity, and body mass index (see “Demographics Form” attachment). A potential risk is discomfort at disclosing this information. It will be made clear that participants can choose not to disclose any of this information if they are not comfortable doing so.

Eating-Related Questionnaires: TFEQ to measure food-related behaviors including restraint, disinhibition, and hunger²⁹; PFS to assess the drive to eat palatable foods in the absence of

energy need or “hedonic hunger”³⁰; FCQ to assess food-related cravings³¹; Disgust Scale-R to measure disgust; and EAT-26 to assess risk for eating disorders³².

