fMRI data will be processed with Statistical Parametric Mapping (SPM8, Wellcome Dept. Cognitive Neurology) in Matlab 7.14. All data initially will be visually inspected for motion, field homogeneity and reconstruction errors, at least bi-weekly to ensure that scans with poor quality can be replaced. We typically observe excess movement (> 2 mm) in 1 out of every 15 scans. Data from each participant will be realigned, normalized to the Montreal Neurological Institute (MNI) template using a gray-matter-segmented IR-EPI as an intermediate, and smoothed with an 8-mm full width at half maximum Gaussian kernel to improve signal-to-noise ratio and account for non-independence on neighboring voxels. After preprocessing, a 128-second high-pass filter will be applied to remove low-frequency fluctuation in the BOLD signal. To account for intersubject/intrasubject variability, a random effects statistical model will be utilized. To generate this model in SPM8, statistical parametric maps will be generated for each subject using the general linear model to describe data variability on a voxel by voxel basis. The hemodynamic response will be modeled with a double gamma function, without temporal derivatives. Hypotheses expressed in terms of model parameters will be assessed at each voxel with univariate statistics, yielding an image whose voxel values comprise a statistical parametric map⁴⁷. For visual food cues tasks (pre- and post-intervention), first-level parametric maps will be entered into a second-level repeated measures ANOVA, in which group effects (change in high-calorie>objects and basics>objects from pre- to post-intervention) will be examined with directional t-contrasts. For correlations noted above, % signal change reflecting activity for each participant will be extracted at the local maximum for each region of interest (insula/ventral

striatum). Relationships between change in neuronal response during the visual food cues task from pre- to post-intervention and (1) eating behaviors, (2) body composition, and (3) neuronal response during IP will be determined using correlations in SPSS version 21.0 (IBM Corp., Armonk, NY), as will the relationship between neuronal response during IP and subsequent eating behaviors. Differences in eating behavior measures between groups (IP vs. control) will be performed using independent samples t-tests in SPSS.

G. Summarize Knowledge to be Gained:

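### The planned brain–eating correlations state no arm term; if the arms are pooled and priming shifts both measures, arm effects mix with the within-arm link (minor, cheap to fix)

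*Combined protocol and SAP*

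**What the plan says.** The Data Analysis Plan (section IV.F) first sets out the arm comparisons. Change in brain response to food cues goes into a second-level repeated measures ANOVA with group contrasts. For eating, "Differences in eating behavior measures between groups (IP vs. control) will be performed using independent samples t-tests in SPSS".

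The same section then plans three kinds of association. It lists "Relationships between change in neuronal response during the visual food cues task from pre- to post-intervention and (1) eating behaviors", followed by body composition and brain response during IP, as relationships to be "determined using correlations in SPSS version 21.0 (IBM Corp., Armonk, NY), as will the relationship between neuronal response during IP and subsequent eating behaviors". Signal change is extracted for every participant, with no restriction to one arm. No partial correlation, arm term, within-arm analysis or interaction is mentioned there or elsewhere.

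Timing matters here. Under Study Design and Research Methods (IV.C), "After baseline measurements, participants will be randomly assigned to either the (a) active group or (b) control group in a 1:1 ratio". The priming scan, the post-priming food-cue scan and the ad libitum lunch all come later. Two kinds of measure come before randomisation. Section IV.C says "Also during the initial baseline visit, participants will be asked to complete several food/eating-related questionnaires", and the body composition entry in IV.D says "Fat mass and fat-free body mass will be measured at baseline, prior to the fMRI study day".

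**The concern.** The trial is run to find out whether priming moves both variables. Section II says "we will assess how priming alters brain responses to food and food intake". If it does, active and control participants differ on average in both neural change and intake. A plain correlation over everyone then has two sources: the distance between the two arm means, and the link among people who received the same primes. The first can add to the second or cancel it, depending on the directions of the arm effects.

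At stake is how the brain–eating link is interpreted. A pooled value could be read as brain response tracking eating among people given the same primes, when part of it only restates that both measures differ by arm. A real within-arm link could also be hidden. Two of these correlations are the plan's only analyses that connect brain response with eating. The third, neural change with response during IP, is brain with brain.

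**Working it through.** **Inputs from the documents.** Allocation is 1:1 (IV.C), so the product of the two arm shares is 0.5 × 0.5 = 0.25. The plan gives no sample size, effect size, expected correlation or significance level for this analysis, so there is no figure of its own to reproduce.

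**Assumed inputs.** Arm effects dB (brain) and dY (eating) of 0.3, 0.5 or 0.8 within-arm SDs; a within-arm correlation ρ of 0 or 0.30, equal in both arms; equal within-arm SDs; 20 per arm; two-sided 0.05.

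**Formula.** For two equal arms pooled,

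r_pooled = (ρ + 0.25·dB·dY) / √[(1 + 0.25·dB²)(1 + 0.25·dY²)].

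**No within-arm link (ρ = 0), equal shifts in the same direction.**
- 0.3 SD: 0.0225 / 1.0225 = 0.022
- 0.5 SD: 0.0625 / 1.0625 = 0.059
- 0.8 SD: 0.16 / 1.16 = 0.138

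Opposite shifts give the same values with a minus sign. Unequal shifts of 0.8 and 0.3 give 0.06 / √(1.16 × 1.0225) = 0.055. If only one measure is shifted, the result is 0.

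**Within-arm link of 0.30.**

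| Shift on both | Same direction | Opposite direction |
|---|---|---|
| 0.3 SD | 0.3225 / 1.0225 = 0.315 | 0.2775 / 1.0225 = 0.271 |
| 0.5 SD | 0.3625 / 1.0625 = 0.341 | 0.2375 / 1.0625 = 0.224 |
| 0.8 SD | 0.46 / 1.16 = 0.397 | 0.14 / 1.16 = 0.121 |

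If only the brain measure is shifted, by 0.8 SD, the result is 0.30 / √1.16 = 0.279. The link is slightly attenuated and none is created. This is the position for body composition and the baseline questionnaires.

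**How often p<0.05 (simulation, 40,000 trials per setting, 20 per arm).**

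| Setting | Plain correlation | With arm included |
|---|---|---|
| ρ = 0, 0.3 SD on both | about 5% | about 5% |
| ρ = 0, 0.5 SD on both | 6–7% | about 5% |
| ρ = 0, 0.8 SD on both | about 14% | about 5% |
| ρ = 0, 0.8 and 0.3 SD | about 6% | about 5% |
| ρ = 0.30, opposite 0.5 SD | about 28% | about 47% |
| ρ = 0.30, opposite 0.8 SD | about 10% | about 47% |
| ρ = 0.30, same direction 0.5 SD | about 60% | about 47% |

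With no link and 0.8 SD on both, the plain rate depends on size: about 9% at 10 per arm, 11% at 15 and 28% at 50.

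**The case against.** The strongest reply is that the harm needs three things the documents do not establish: pooled arms, an eating measure taken after priming, and sizeable arm effects on both variables.

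- **Pooling is not stated.** Extraction for every participant makes it the natural reading for neural change with eating. However, the section introduces its correlations as already mentioned, and no earlier text in this document describes them, so the intended scope is uncertain. The section also uses IP as the label of the active arm. Response during IP may therefore mean that arm alone, and then the two correlations using it carry no arm mixing. This stands.
- **The eating measures are not listed.** The between-group test of eating behaviour points to intake after priming. Section IV.D, though, describes the "TFEQ to measure food-related behaviors including restraint, disinhibition, and hunger", and that questionnaire is completed before randomisation. Arm cannot shift it. This stands.
- **Inflation is small.** It is near nominal at 0.3 SD and 6–7% at 0.5 SD. This is a pilot in which staying for lunch appears optional, so numbers with intake data may be low and the inflation lower still. This stands for false positives. Masking is larger, but it needs arm effects that run against the within-arm link, which is also an assumption.
- **A pooled correlation is a valid description of the two arms together,** and the plan nowhere claims a within-arm or mediating link. This is true, and it makes the point one of interpretation rather than an invalid test.
- **Adjustment has its own assumption.** A single arm-adjusted estimate takes the slope as equal in arms that saw different primes. This is fair, and the fix allows for it.

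A reader might infer that arm confounds every planned correlation, or that the trial's arm comparisons are biased. The documents support neither. Baseline partners cannot acquire a spurious link from arm, and the ANOVA contrasts and t-tests do not use these correlations.

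**Conclusion.** The point holds in limited form and is minor. The plan states no arm term for correlations in which both variables can be measured after randomisation; neural change with intake after priming is the clearest. If the arms are pooled and priming shifts both, the plain correlation departs from the within-arm link in either direction. At an assumed 20 per arm the false-positive rate stays near 5–7% for shifts up to 0.5 SD and reaches about 14% at 0.8 SD on both. Detection of a 0.30 link can fall from about 47% to about 28% with opposite 0.5 SD shifts. All of these sizes rest on assumed effects, sample size and a common within-arm correlation. The two correlations using response during IP are affected only if both arms enter them. The documents do not rank these analyses as secondary; that they support the arm comparisons is an inference from their place in the plan.

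**What to change.** For each pair in which both measures are taken after randomisation and both arms are used, replace the plain correlation with a partial correlation, or a regression that includes arm. Show the within-arm estimates descriptively, and examine an arm-by-brain interaction as exploratory, since the adjusted estimate assumes a common slope.

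In the same edit, state which measures count as eating behaviours and whether response during IP is analysed in both arms or the active arm only. If the active arm only, no arm term is needed for those two correlations. Correlations with body composition and baseline questionnaires need no change on this ground.

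The cost is SAP wording and one degree of freedom per adjusted analysis, with no new data; the exploratory interaction uses one more in its own model. Within-arm estimates will be imprecise: at an assumed 20 per arm, the 95% interval around r = 0 is ±tanh(1.96/√17), about −0.44 to 0.44.
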